Indeed, the results of SYNTAX, as well as the numerous other trials discussed above suggest equipoise between PCI with first generation DES and CABG for the composite of mortality,

myocardial infarction or stroke, albeit with higher rates of repeat revascularization for PCI.

Although the importance of mortality, MI and stroke as essential endpoints is universally accepted, no single trial has been adequately powered to examine whether CABG has superior, comparable, or non-inferior rates of the composite endpoint of mortality, MI, or stroke compared expressed that the inclusion of unplanned revascularization into the primary SYNTAX endpoint (which was necessitated for sample size requirements) biased the trial against PCI, as many other endpoints of equal or more important impact to patient well-being might have been selected instead. As discussed above, most trials (including SYNTAX) have shown that stroke rates are higher after CABG than PCI, an endpoint significantly more important to physicians and subjects than repeat revascularization. Peri-procedural bleeding is significantly more common after CABG compared to PCI, and is a powerful independent predictor of early and late mortality in this setting.^{38, 39, 40}Subjects undergoing CABG compared to PCI have prolonged hospital stays (for example, mean 3.4 days after PCI vs. 9.5 days after CABG, P<0.001),⁷ greater and prolonged incisional chest pain, and delayed return to work and activities of daily life. The impact of all of these adverse events, including the benefits from the greater prevention of recurrent ischemia and repeat revascularization with CABG compared to PCI, may be captured in quality of life measures. As reported from the One-Year Quality of Life SYNTAX Substudy,⁴¹

PCI as compared to CABG had superior measures of quality of life in most measures at one month, though these outcomes had equalized by 6 and 12 months (Figure 2.5).

Figure 2.5 SYNTAX Trial: Quality of Life Measures Comparing PCI and CABG

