9.3.2. Quality of Life

HRQoL and functional status will be assessed using a combination of generic and diseasespecific measures selected to cover a broad range of health domains that may be affected by coronary artery disease, its treatment, and its complications in about 1800 patients. Diseasespecific QoL will be assessed using the Seattle Angina Questionnaire (SAQ)^{77, 78} and the London School of Hygiene Dyspnea Questionnaire.^{79, 80} Mental health and depression will be assessed using the Patient Health Questionnaire-9 (PHQ-9).⁸¹ Generic health status will be assessed using the Medical Outcomes Study 12-item Short Form (SF-12),⁸² and health utilities will be assessed using the EuroQoL (EQ-5D) with U.S.-specific weights.^{83, 84} Further details regarding the rationale for selection of these instruments and specific analytic approaches are detailed in Section 17. These measures will be assessed using standardized, written questionnaires at baseline (prior to randomization), 1 month, 12 months, 3 years, and 5 years.

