If there are no significant differences in prognostically important endpoints (e.g., death, non-fatal MI, non-fatal stroke) between the two groups then the analysis will be based on the observed cost and QoL data from the trial itself (under the assumption that long-term survival would be comparable for the two groups). If there are differences in one or more of these endpoints (or their composite), however, then it will be important to account for differences in long-term survival between the two groups in the analysis. In this case, the data from the trial itself will be used along with external data in order to project long-term survival for each trial participant and use these estimates in order to estimate differences in quality-adjusted life expectancy over each subject's lifetime. Consistent with current guidelines for health economic analyses, the trial data will be used to calculate an incremental cost-effectiveness ratio (cost per quality-adjusted year of life gained) for the more expensive technique compared with the less expensive technique, and by comparing this ratio with those for other medical interventions, determine whether one treatment strategy is preferred on economic grounds.⁸⁵ Additional analyses will be performed using intermediate, disease-specific endpoints including cost per major adverse cardiovascular event avoided and cost per repeat revascularization avoided.⁸⁶

The primary cost-effectiveness and quality of life analyses will be performed when all randomized subjects have completed a minimum of 3-years of follow-up. Although this time frame is slightly different from that for the main clinical endpoint, the longer follow-up duration for the economic analysis will minimize the need for extrapolation beyond the observed data.

Additional details of the approaches to U.S.-specific costing and the formal cost-effectiveness analysis are provided in Section 17.4 and Section 17.5.

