17.5. Analytic Plan

17.5.1. Quality of Life Endpoints

Since quality of life is a multidimensional construct for which different subjects may have different individual preferences, no specific scale will be considered as the "primary" QoL endpoint of the EXCEL trial. Rather, the goal of the study will be to describe any differences in the various quality of life scales over the time-frame of the trial. To limit any "false positive" results due to the large number of scales and timepoints evaluated, all QoL analyses will be performed using a p-value of <0.01 as an indicator of statistical significance.

For each of the quality of life measures in this study, data analysis will proceed in two stages. First, a simple descriptive and comparative analyses of cross-sectional data by intention-to-treat will be performed. For these cross-sectional analyses, comparisons will be performed at each follow-up timepoint using analysis of covariance to adjust for any baseline differences, including baseline score, between the treatment groups. Second, in order to account for missing data, longitudinal random coefficient growth curve models will be used to examine the effect of CABG versus PCI over time on each health status/QoL outcome. These models readily accommodate linear and nonlinear changes over time, as well as missing data patterns commonly seen in longitudinal studies. These analyses will incorporate all available QoL scores including those for subjects who die, withdraw from the study, or are lost to follow-up. Variables included in the longitudinal models for each outcome will include treatment (according to intention to treat), follow-up time (using linear, quadratic, and cubic terms), and interactions between treatment and each time term. In addition, these analyses will adjust for any baseline sociodemographic and clinical factors that differ between the two groups.

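### Read plainly, the cubic-in-time quality-of-life model in Protocol 17.5.1 returns only about 0.44 of the expected 1-month PCI–CABG difference and places about 0.49 of it at baseline

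*Protocol*

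**What the plan says.** Protocol 17.5.1 analyses each QoL scale in two stages. The first compares the arms at each follow-up visit by analysis of covariance, with baseline score among the adjustments. The second is introduced to deal with missing data: "longitudinal random coefficient growth curve models will be used to examine the effect of CABG versus PCI over time". Its terms are treatment, "follow-up time (using linear, quadratic, and cubic terms), and interactions between treatment and each time term". On the data entering it, the section says: "These analyses will incorporate all available QoL scores including those for subjects who die, withdraw from the study, or are lost to follow-up". On covariates, "these analyses will adjust for any baseline sociodemographic and clinical factors that differ between the two groups"; baseline score, named for the first stage, is not named here. No visit factor, knot, time transformation or check of fit is mentioned. Section 17.5.2 reuses the same time terms.

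Protocol 9.3.2 sets the assessments "at baseline (prior to randomization), 1 month, 12 months, 3 years, and 5 years". Section 2.6 reports that in SYNTAX, PCI "had superior measures of quality of life in most measures at one month, though these outcomes had equalized by 6 and 12 months". On timing, 9.3.3 states: "The primary cost-effectiveness and quality of life analyses will be performed when all randomized subjects have completed a minimum of 3-years of follow-up".

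SAP 2.3.4 leaves QoL analyses to another document. SAP Appendix A plans only means and standard deviations, at baseline, 1, 6 and 12 months and 3 years. Within these two documents, Protocol 17.5 is therefore the only specification of the longitudinal model.

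**The concern.** The between-arm difference most expected in this trial is brief: present at 1 month and gone within the first year. On a 60-month axis it must rise and fall within the first fifth of the range. The cubic gives the between-arm difference four coefficients (treatment plus three interactions) to describe five visits. The shape it lacks is almost exactly the contrast between month 0 and month 1.

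At stake is the QoL comparison at the visit where it matters most. The growth model is also the analysis a reader would turn to when questionnaires are missing. It would understate the early difference and show an imbalance at baseline. With time measured from 0 and uncentred, its treatment coefficient is the fitted baseline difference itself.

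**Working it through.** The documents give no QoL effect size, standard deviation (SD), power or fitted curve, so there is no planned figure to reproduce. Let d be the true 1-month difference and express everything as a fraction of d.

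**Inputs.** Visits t = 0, 1, 12, 36, 60 months (Protocol 9.3.2). Mean structure: cubic in t within each arm (17.5.1). Expected differences: (0, d, 0, 0, 0), reading Section 2.6 as no difference from 12 months on.

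**Formula.** Five points and a cubic leave one direction that cannot be fitted, with elements c_j = 1 / Π(t_j − t_k), the product running over k ≠ j. The least-squares fit removes that component: fitted_j = y_j − c_j (Σ c_k y_k) / Σ c_k². With y equal to d at month 1 and 0 elsewhere, the fit at month 1 is d(1 − c_1²/Σc²), and at any other visit it is −d c_j c_1/Σc².

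| Month | Π(t_j − t_k) | c_j × 10^5 | c_j² × 10^10 | Fitted difference |
|---|---|---|---|---|
| 0 | 25,920 | 3.858 | 14.884 | 0.489 d |
| 1 | −22,715 | −4.402 | 19.381 | 0.442 d |
| 12 | 152,064 | 0.658 | 0.432 | 0.083 d |
| 36 | −725,760 | −0.138 | 0.019 | −0.017 d |
| 60 | 4,078,080 | 0.025 | 0.001 | 0.003 d |

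Σc² × 10^10 = 34.717. Month 1: 1 − 19.381/34.717 = 0.442. Month 0: 3.858 × 4.402/34.717 = 0.489. The 1-month difference is cut by 56%.

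**Random effects.** Generalized least squares with a random intercept, intercept and slope, or intercept, slope and quadratic gives the same fractions with complete data.

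**Few subjects at 60 months.** If accrual is uniform over 29 months, about (29 − 24)/29 = 17% have reached 60 months when the last subject reaches 36. Giving month 60 weight w in least squares replaces its 0.0006 in Σc² by 0.0006/w. Even at w = 0.01 the sum rises only to 34.776, and month 1 becomes 1 − 19.381/34.776 = 0.443. So 1% of subjects with 60-month data is enough to keep the distortion.

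**Other variations, as baseline / 1 month / 12 months.**
- Monotone dropout: 0.488 / 0.443 / 0.093.
- Visit-window jitter: 0.489 / 0.443 / 0.092.
- Arms also differing by up to 0.3 d at later visits: the baseline error is 0.48 to 0.51 d and the 1-month shortfall 0.54 to 0.58 d.

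**SAP visit list (0, 1, 6, 12, 36).** The products are 2,592, −1,925, 5,400, −19,008 and 907,200. The fit is 0.44, 0.41, 0.21, −0.06 and 0.00 of d. With 60 months added, baseline is 0.46 and 1 month 0.40.

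**Readings under which the problem goes away.** With visits 1, 12, 36, 60 (baseline only a covariate) or 0, 1, 12, 36 (data cut at 36 months), four coefficients fit four visit differences exactly: 1.00 d at 1 month and 0 elsewhere. On a log(1+t) scale the 1-month fit is 0.91 d and the baseline fit 0.05 d.

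**Chance of a significant false baseline difference at the plan's 0.01 level.** Assume 900 per arm (1,800 randomized 1:1), a two-sided test, complete data and half the baseline variance between subjects. The standard error of the fitted baseline difference is then 0.0418 SD. For d = 0.3 SD, z = 0.489 × 0.3/0.0418 = 3.51, giving about 83%. For d = 0.1, 0.2 and 0.5 SD the chance is about 8%, 41% and 99.9%. At 12 months it is about 2% for d = 0.3 SD and 5% for d = 0.5 SD.

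**After the fix.** Visit-by-treatment terms return 1.00 d at 1 month and an expected 0 at the other visits.

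**The case against.** The strongest reply is that the result depends on a reading that 17.5.1 never states outright. If baseline score is only a covariate, or the primary analysis uses data to 36 months on the protocol schedule, the cubic is saturated and exact at every visit. That is correct, and it limits the point. The text nevertheless leans the other way. It takes in all available scores, names baseline score as a covariate only for the first stage, and sets no 36-month cut-off although some subjects will have 60-month scores by then. On the SAP's list, stopping at 3 years does not help because the 6-month visit restores the missing degree of freedom.

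A second reply is that the first stage already estimates the 1-month difference directly, that no QoL scale is primary, and that QoL carries no powered hypothesis. This also stands. The early comparison is not lost; the fault is confined to the growth model. It still leaves two planned analyses that contradict each other at 1 month. SAP 2.3.4 points to a further document that may settle the matter, but it is not among those available. Protocol 17.6 allows changes for unanticipated data or results, whereas this pattern is anticipated in Section 2.6.

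A third reply is that the pattern itself is assumed. Section 2.6 speaks of most measures and gives no sizes, so only the fractions of d are firm. It supports a between-arm difference, not any particular course within an arm.

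**Conclusion.** The point holds, conditionally. With baseline score as a response, untransformed time and the protocol's five visits, the second-stage model returns about 0.44 of the true 1-month difference and about 0.49 of it at baseline. This does not depend on the random-effects structure, on how many subjects reach 60 months, or on moderate dropout. It does rest on the SYNTAX-like pattern and on the reading of 17.5.1 just stated.

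Four stronger conclusions might be inferred and are not supported:
- *A material false difference at 12 months.* The leakage is about 8% of d and would seldom reach p < 0.01.
- *A 1-month estimate resting on the roughly 17% with 60-month data.* When baseline is a covariate the fit at 1, 12 and 36 months is exact however few reach 60 months. Sparse 60-month data weaken only the 60-month estimate and the shape between visits.
- *Unusable values between visits.* A cubic through 0, 1, 12 and 36 months does swing widely between them, to about 2.8 d near month 5 and −9.5 d near month 27. No section plans to read the curve there, and 17.5.4 and 17.5.5 do not call on it.
- *Bias in 17.5.2.* Interpretation there rests on the coefficients for clinical events, and no bias in those has been shown.

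This is a correction that should be made to a secondary, descriptive analysis. It does not threaten the trial's main conclusions.

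**What to change.** In Protocol 17.5.1, replace the linear, quadratic and cubic time terms with scheduled visit as a categorical factor and a visit-by-treatment interaction. Include baseline score as a covariate, or as a response with its mean constrained equal across arms, and state which. Use an unstructured within-subject covariance. The likelihood-based handling under missing at random, and the sensitivity analyses for missing QoL data already planned, stay as they are.

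The cost is a wording change and, on either document's five-visit schedule, at most one more mean parameter per arm (five visit means in place of four cubic coefficients). No extra data are needed. The same edit should settle which visit list applies, since the SAP adds 6 months and the protocol does not. Using the same visit terms in 17.5.2 is optional, for consistency only.

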9.1.9. Measures Taken to Minimize Bias

9.1.9.1. Randomization

Assessment of eligibility must be done prior to randomization. Suitable subjects will be randomized to procedure with PCI or CABG in a ratio of 1:1. Randomization will be stratified by medically treated diabetes mellitus (diabetic vs. non-diabetic), SYNTAX score (<23 vs. \geq 23) and by center.

The randomization will be managed by a central IVRS randomization. See Section 7.2.12 for randomization details. Once randomized the subject is analyzed as part of the intent-to-treat (ITT) population.

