17.2. Subject Population

The population for the quality of life and cost-effectiveness sub-studies will consist of 1800 subjects. The primary analyses will be conducted on an intention-to-treat (ITT) basis. In particular, any subjects who die prior to receiving their initial revascularization procedure will be retained in the ITT analyses and considered as part of their randomization group. Secondary analyses will be performed based on the per-protocol population (i.e., sub-study subjects who receive their assigned treatment) and a treatment-received population (sub-study subjects based on the initial revascularization procedure performed).

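### The quality-of-life models choose covariates by chance imbalance between arms instead of from a fixed prognostic set, which gives up a modest amount of precision and leaves the covariate list open until baseline data by arm are seen.

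*Protocol*

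**What the plan says.** Protocol 17.5.1 plans two analyses for each QoL measure.

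- **Cross-sectional.** Arms are compared at each follow-up time "using analysis of covariance to adjust for any baseline differences, including baseline score, between the treatment groups".
- **Longitudinal.** Random-coefficient growth curves contain treatment, "follow-up time (using linear, quadratic, and cubic terms), and interactions between treatment and each time term". The section then adds that "these analyses will adjust for any baseline sociodemographic and clinical factors that differ between the two groups".

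Neither analysis has a covariate list, or a test or threshold for deciding that a factor differs. The same section says that "all QoL analyses will be performed using a p-value of <0.01 as an indicator of statistical significance" and names no primary QoL scale. Section 17.2 sets the size: "The population for the quality of life and cost-effectiveness sub-studies will consist of 1800 subjects".

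Nothing else fixes the covariates for this comparison. SAP 2.3.4 leaves the QoL analyses to be described elsewhere. By contrast, SAP 3.6.1.3 names its candidate covariates for the clinical composites and chooses them on prognostic grounds (with a stepwise option). The exploratory QoL model in Protocol 17.5.2 includes a broad baseline set with no imbalance condition.

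**The concern.** Allocation is random, so a baseline factor that differs between arms does so by chance. A covariate improves precision through its relation to the outcome, whether or not it is imbalanced. A rule driven by imbalance therefore lets in factors that may be unrelated to QoL and leaves out prognostic ones that happen to be balanced. Treated diabetes and SYNTAX score (<23 vs ≥23) are stratification factors (Protocol 9.1.9.1). They are kept close to balance by design, so the rule would seldom select them and the analysis would usually omit factors used in the randomisation.

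The second issue is pre-specification. With no definition of a difference, the model cannot be written down before baseline data by arm are tabulated, and someone then has to judge which differences count. The trial is open-label (SAP 2.8), and the primary QoL analysis waits until every subject has at least three years of follow-up, later than the main clinical analysis (Protocol 9.3.3). Baseline tables by arm will by then be familiar. At stake are some power under a strict 0.01 criterion and the credibility of the adjusted results.

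**Working it through.** The documents state no QoL effect size, SD, explained variance or power, so there is no planned figure to reproduce. The check compares the planned rule with a fixed covariate set.

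**Inputs from the documents.** 1800 subjects (Protocol 17.2) at 1:1 (Protocol 9.1.9.1) give n = 900 per arm. The significance level is 0.01 (17.5.1), taken as two-sided because the sidedness is not stated.

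**Assumptions.** Baseline score explains 25% of outcome variance. Fifteen other independent candidates together explain a further 5%, 10% or 20%. A factor counts as differing when p < 0.05. All 1800 subjects contribute.

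**1. What the rule selects.** Each independent candidate has a 5% chance of selection. With 15 candidates, 15 × 0.05 = 0.75 are expected to enter, and the chance of at least one is 1 − 0.95^15 = 54%. With 20 candidates these are 1.0 and 64%. Most prognostic covariates are left out.

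**2. Value of fixed covariates.** For an effect of d SD and explained variance R², power = Φ( d / √(2(1 − R²)/n) − 2.576 ).

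The effect giving 80% power unadjusted is d = (2.576 + 0.842) × √(2/900) = 0.161 SD. At that effect, power is 82.4%, 84.8%, 89.3% and 93.4% for R² of 5%, 10%, 20% and 30%.

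**3. Planned rule against a fixed set, baseline score in both.** For each case the effect is set so that the fixed set has 80% power: d = (2.576 + 0.842) × √(2(1 − 0.25 − R²other)/900). The rule was simulated with 4,000 trials per case (Monte Carlo standard error about 0.7 points). As a hand check, the formula is also evaluated with the baseline score alone in the model (R² = 0.25).

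| Variance explained by other covariates | Effect (SD) | Fixed set, simulated | Planned rule, simulated | Formula, baseline score only | Loss (simulated) |
|---|---|---|---|---|---|
| 5% | 0.135 | 80.1% | 77.4% | 76.6% | about 3 points |
| 10% | 0.130 | 79.8% | 73.0% | 72.8% | about 7 points |
| 20% | 0.119 | 79.4% | 64.7% | 63.7% | about 15 points |

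The planned rule performs almost as if no covariate other than the baseline score had been used.

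**4. Larger effects.** At 0.2 SD, unadjusted power is Φ(0.2/0.0471 − 2.576) = Φ(1.67) = 95%. With the baseline score alone it is 99.0%. Adding covariates that explain 5%, 10% or 20% takes it to 99.4%, 99.6% or 99.9%, so the loss is below one point.

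**5. Type I error.** With no true effect (8,000 trials per case), the rule with baseline score retained rejected in 1.01%, 0.69% and 1.01% of trials, against 1.08%, 0.74% and 0.89% for the fixed set. There is no inflation when the rule is applied mechanically.

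**The case against.** The other side has several good points.

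- **Baseline score.** A reader might infer that the plan gives up the baseline score, usually the strongest covariate. If it entered only when it differed, the same simulation gives 63%, 58% and 49% power against about 80%. The documents do not support that reading. The covariance analysis adjusts "using analysis of covariance to adjust for any baseline differences, including baseline score", most naturally meaning that the score is always included. The growth-curve model uses all available QoL scores, and baseline is a scheduled assessment (Protocol 9.3.1), so the score can enter there as a response.
- **General lack of power.** A reader might infer that the sub-study is underpowered without further covariates. At the planned 900 per arm and 0.2 SD it is not.
- **A model that changes by scale and visit.** Selection is on baseline factors common to all scales, and the growth curve covers all visits at once. One baseline table gives essentially one list, apart from each scale's own baseline score and missing data.
- **Bias or false positives.** Nothing says that covariates are chosen after looking at outcomes, and step 5 shows no inflation. In an open-label trial there is also no unblinding event until which the list stays open; the relevant moment is when baseline data by arm are seen.
- **A separate plan.** SAP 2.3.4 defers QoL analysis, and Appendix B describes its plans as general. A fixed list may exist elsewhere, but it is not in these documents.

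These points limit the size of the problem. They do not defend choosing covariates by imbalance.

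**Conclusion.** The concern stands as a modest, avoidable weakness. Both QoL models select covariates on chance imbalance with no definition of a difference, and nothing in the protocol or SAP replaces that rule for the treatment comparison. Precision is forgone only on prognostic covariates other than the baseline score. The cost is about 3 to 7 points of power if these explain 5-10% of variance and up to about 15 points if they explain 20%, for effects near the limit of detection; it is negligible at 0.2 SD or more. The size rests on the assumed explained variances, number of candidates, 0.05 threshold and full completion. The direction does not, provided that the omitted covariates are prognostic.

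The pre-specification weakness is discretion over which baseline differences count, not a demonstrated error-rate problem. QoL has no primary scale, its stated aim is descriptive, and trial success (SAP 2.7) does not depend on it. The change is still worth making, because results will be declared significant at 0.01 and a better method is available at no data cost.

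**What to change.** In Protocol 17.5.1, and in any separate QoL analysis plan, replace the imbalance rule in both the cross-sectional and the longitudinal models with one fixed set:

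- the baseline score of the scale (as a covariate, or as a response in the growth-curve model, stating which);
- the randomisation strata: treated diabetes, SYNTAX <23 vs ≥23, and centre grouped by region (SAP 3.9.2 already defines regions);
- age and sex.

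Specify the set before any QoL data by arm are examined and use it for every scale. If adjustment for observed imbalances is still wanted, keep it only as a sensitivity analysis with a stated criterion for a difference. The cost is a change of wording; all the variables are already collected.

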15.3. Major Adverse Event Rates in Left Main Studies

Long term adverse event data for PCI in the LM population has not been extensively studied or reported and is therefore not provided in the risk analysis section. Recent literature on major cardiac event rates in left main procedures^{1,2,3,4,5,6,7,8} is limited and emerging. In trials conducted in patients with LM disease treated with either PCI or CABG, the following range of major adverse event rates were observed: death (2.0% at one year to 11.2% at 5 years), myocardial infarction (1.0% at one year to 15.7% at 5 years), stroke (0.1% at one year to 5.9% at 5 years) and revascularization (3.4% at one year to 19.7% at 5 years).

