A particular challenge in the analysis of quality of life data relates to the problem of missing data (due to death, incapacity, subject refusal, or loss to follow-up). The proposed analytic strategy assumes that measurements are missing at random, however it is possible that subjects with impaired quality of life may be less likely to complete the interview. The sensitivity of the results to a variety of alternative assumptions regarding the relationship between quality of life and the likelihood of completing the QoL questionnaires will be examined. Potential approaches will include imputing missing values with the natural "worst case" score for each of the quality of life endpoints and application of multiple imputation techniques.¹⁶⁹

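### Quality-of-life scores after death are handled as missing at random alongside refusal and loss to follow-up, so the 3- and 5-year growth-curve estimates match neither a while-alive nor a death-inclusive target

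*Protocol*

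**What the plan says.** Protocol section 17.5.1 analyses each QoL scale in two stages. The first is a cross-sectional analysis of covariance at each follow-up visit. The second is longitudinal: "longitudinal random coefficient growth curve models will be used to examine the effect of CABG versus PCI over time". On subjects who die, the section says: "These analyses will incorporate all available QoL scores including those for subjects who die, withdraw from the study, or are lost to follow-up". No rule is given for the time after death.

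The same section then describes missing data as arising "due to death, incapacity, subject refusal, or loss to follow-up", and continues: "The proposed analytic strategy assumes that measurements are missing at random". It commits to a sensitivity analysis: "The sensitivity of the results to a variety of alternative assumptions regarding the relationship between quality of life and the likelihood of completing" the questionnaires will be examined. The methods are offered only as possibilities: "Potential approaches will include imputing missing values with the natural" worst score, and multiple imputation.

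Other relevant places:
- Protocol 17.2 makes the sub-study analyses intention-to-treat and keeps subjects who die before their procedure, but assigns them no QoL score.
- Protocol 17.5.2 adds model terms for MI, stroke and repeat revascularization, but none for death.
- Protocol 17.5.4 and 17.5.5 bring survival in through QALYs and life-years, for cost-effectiveness.
- SAP 2.3.4 leaves QoL analysis to be described elsewhere. SAP Appendix A plans means and standard deviations of the scales without saying how deaths enter.

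**The concern.** A score that a refuser did not give exists and could have been observed. A score after death does not exist. Missing at random is a usable assumption for the first case; for the second it defines a hypothetical quantity, namely the QoL the dead would have had if they had lived. A growth-curve model fitted under that assumption estimates the arm means in a population where nobody dies.

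The cross-sectional analysis, by contrast, can only use those who are alive and respond. The two planned stages therefore answer different questions at 3 and 5 years, and the plan names neither question. If mortality differs between arms, a reader cannot tell whether a reported difference includes, excludes or projects past the deaths. These comparisons are judged at p<0.01 and will be reported as the trial's QoL findings.

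**Working it through.** The documents give no power, effect size or sample-size figure for QoL, so there is no plan figure to reproduce. The calculations below are illustrations.

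**Inputs from the documents**
- Sub-study size 1800 (Protocol 17.2), about 900 per arm.
- Significance level p<0.01 (Protocol 17.5.1), taken as two-sided: critical value 2.58.
- 3-year mortality of 9.0% CABG and 3.7% PCI in the SYNTAX left main subgroup with scores 0–32 (Protocol Table 2-2).
- SF-12 mean 50 and SD 10 (Protocol 17.3.2), range 0–100 (Protocol 9.3.1).

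**Assumed:** survivor EQ-5D mean m of 0.80–0.85 and SD 0.2, equal survivor means in both arms, no other dropout, and death scored 0.

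**EQ-5D at 3 years.** With mortality d in an arm, the mean with deaths scored 0 is (1−d)m. The shift in PCI minus CABG is (d_CABG − d_PCI)·m. The variance in an arm is (1−d)·0.04 + d(1−d)·m².

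*9.0% versus 3.7%*
- m = 0.80: shift 0.053 × 0.80 = 0.0424. Variances 0.0888 and 0.0613. SE = √(0.1501/900) = 0.0129. Ratio 3.3.
- m = 0.85: shift 0.053 × 0.85 = 0.0451. Variances 0.0956 and 0.0643. SE = √(0.1598/900) = 0.0133. Ratio 3.4.

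*8% versus 6%*
- m = 0.80: shift 0.0160. Variances 0.0839 and 0.0737. SE 0.0132. Ratio 1.2.
- m = 0.85: shift 0.0170. Variances 0.0900 and 0.0783. SE 0.0137. Ratio 1.2.

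*Equal mortality:* shift 0.

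**SF-12 cross-check, same mortality.** With death scored 0 the difference is 0.053 × 50 = 2.65 points, SE 0.73, z 3.6. With death placed at an assumed floor of 20 it is 1.59 (z 2.8), and at 30 it is 1.06 (z 2.1). At 9% versus 7% with death scored 0 it is 1.0 (z 1.3). For scale, among survivors the SE is 10·√(2/900) = 0.47, so p<0.01 needs about 1.21 points.

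**What missing at random does to the dead.** I simulated 500 trials with 900 per arm, SF-12 scores at baseline, 1 month, 1 year and 3 years, no true QoL difference, and deaths of 9.0% versus 3.7%. Missing 3-year scores were filled by regression on earlier scores within arm, as a stand-in for the growth curve.

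| | Death unrelated to QoL | Lower scorers die more often |
|---|---|---|
| Mean 3-year score projected for dead CABG subjects | 50.0 | 44.9 |
| PCI − CABG, missing at random | about 0.0 | about 0.0 |
| PCI − CABG, survivors only | about 0.0 | −0.3 |
| PCI − CABG, death scored 0 | +2.6 | +2.4 |

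So the dead are given ordinary living scores. The resulting estimate differs from the death-inclusive one and, when sicker subjects die, from the survivors-only one as well.

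**The case against.** **The direction is not fixed.** A reader might infer that the arm with more deaths is always overrated. The documents do not support that, because the protocol sets no death-inclusive target and its stated aim is to describe differences on the scales. Against survivors-only QoL, missing at random rates the higher-mortality arm slightly lower. This stands.

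**The mortality gap is selective.** Table 2-2 comes from a subgroup that Protocol 2.3 calls post hoc and underpowered. The meta-analysis in Protocol 2.4 finds no mortality difference (3-year odds ratio 1.11, 95% CI 0.66 to 1.86). Protocol 15.3 cites "death (2.0% at one year to 11.2% at 5 years", but that is a range across left main studies of either treatment, not a difference between arms. This stands too: the 9.0% versus 3.7% case is an illustration, not a forecast.

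**The size is easily overstated.** Dividing the EQ-5D shift by the survivor-only SE, √(2 × 0.04/900) = 0.0094, would give 4.5–4.8 standard errors. Scoring deaths as 0 also widens the variance, so 3.3–3.4 is the right figure.

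**Death is counted elsewhere.** QALYs and life-years include survival, and mortality by arm is a secondary endpoint at the QoL visits after baseline. That is true, but QALYs serve the cost-effectiveness analysis and do not define what the scale-by-scale comparisons mean. A reader might also assume that EQ-5D death = 0 is already a protocol rule. The documents give a 0–1 utility scale but state no value for death.

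**Sensitivity analysis is promised.** It is, and worst-case imputation would reach the deaths if applied to all missing values. However, it is framed around questionnaire completion, no method is fixed, and it would score living non-responders the same as the dead. Multiple imputation in its usual form would again give the dead living scores.

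**Conclusion.** The point holds in limited form. Section 17.5.1 pools death with non-response under missing at random, so the growth-curve results at 3 and 5 years correspond to no stated target.

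The size depends on the mortality difference. On EQ-5D it is 0.042–0.045 (3.3–3.4 SE, beyond the p<0.01 threshold) at 9.0% versus 3.7%, 0.016–0.017 (about 1.2 SE, well below it) at 8% versus 6%, and zero at equal mortality. These figures rest on the assumed EQ-5D mean and SD, equal survivor means, death scored 0, and 900 per arm with no other dropout. The simulation also rests on its own model for scores and deaths.

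The consequence is confined to the descriptive QoL comparisons, for which the protocol names no primary scale. Nothing here touches the primary or powered secondary endpoints. The change is worth making because it is cheap and replaces an unsuitable assumption with a defined one.

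**What to change.** In Protocol 17.5.1, and in whichever document will hold the QoL analysis plan:

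1. Limit the missing-at-random assumption to subjects alive at the visit. For the growth-curve model this means averaging fitted values over subjects alive at that visit; relabelling alone would leave the projection in place.
2. Label the covariance and growth-curve results as while-alive, and show the proportion dead by arm in the sub-study at each visit beside them.
3. Commit to one supplementary EQ-5D analysis at 1, 3 and 5 years in all sub-study subjects, with death scored 0 and that value stated as a convention.
4. Apply worst-case imputation to living non-responders separately from deaths.

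No new data are needed. The cost is revised wording, one extra table, and QoL reported under two estimands, which the text must explain.
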